7.3.5 Physical Examinations

Not applicable in the study.

7.3.6 Other Safety Assessments

Neurologic Examination data will be listed.

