5.4.2 Safety Endpoints

- (1) Adverse Events and Adverse Drug Reactions
- (2) Neurological Examination
- (3) General laboratory tests
- (4) Vital signs
- (5) Standard 12 lead ECG

[Rationale]

Because delayed neurotoxicity was observed in nonclinical studies of this drug, in addition to general safety endpoints, a neurological examination was included to check for the development of symptoms due to neuropathy of peripheral nerves and notochord.

[figure not shown]
6. Target Sample Size and Study Duration

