The investigator (subinvestigator) will measure all of the following tests at the contract laboratory testing institution on Day4 (before the end of continuous intravenous infusion), Day7, Day10, Day14, Week 3, and at discharge, and record the date of confirmation of test results and the results of confirmation (clinical significance). The test results provided by the contract laboratory testing institution will be retained by the study site and the sponsor.

The test items are as follows.

- Hematology: white blood cell count (WBC), red blood cell count (RBC), hematocrit (Ht),
Hemoglobin (Hb), Platelets (Plt)
- Blood biochemistry: AST (GOT), ALT (GPT), LDH, ALP, γ -GTP,
Total bilirubin (T-Bil), direct bilirubin (D-Bil),
Total cholesterol (T-Chol), triglycerides (TG), total protein (TP),
CK (CPK), Blood urea nitrogen (BUN), Serum creatinine (Cre), eGFR,
Uric acid (UA), Na, K, Cl, albumin, glucose
- Urinalysis (qualitative): Sugar, protein, occult blood

(2) Standard 12 lead ECG

The investigator (subinvestigator) will perform standard 12 lead ECG at baseline and Day4 (before completion of continuous intravenous infusion) to determine whether there are any abnormal findings. The date and time of standard 12 lead ECG, ECG parameters (Heart rate, PR interval, QRS interval, RR interval, QT interval, and QTc interval), and assessment results will be recorded in the CRF. Clinically significant abnormal findings, if determined by the investigator or subinvestigator, should be recorded as adverse events. The investigator will maintain ECG charts as source documents.

(3) Vital signs

The investigator/subinvestigator will measure systolic/diastolic blood pressure, pulse rate, and body temperature (Axillary, oral or tympanic body temperature) before administration, on Day4 (before the end of continuous intravenous infusion), Day7, and Day14, and record the date of measurement and the test results in the case report form. Blood pressure should be measured in the same arm throughout the study period whenever possible. Clinically significant abnormal findings, if determined by the investigator or subinvestigator, should be recorded as adverse events.

(4) Neurological Examination

The Investigator (or Subinvestigator) will perform a neurological examination on the healthy side once from the onset to Day5, and then on Day14, Week 3, at the time of discharge, and 3 months later. The tests that may be

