affected by the subject's condition or treatment (Disturbance of consciousness, speech/articulation disorder, cognitive disorder, urinary catheter, etc.) will be performed on the day of observation, and the date and results will be recorded in the CRF.

NEUROLOGIC EXAMINATION (FUNCTIONAL)

- Sensory tests: Pain, sense of touch, sense of temperature, sense of vibration, sense of position
- Reflex function: Biceps brachii reflex, triceps brachii reflex, patellar tendon reflex, Achilles tendon reflex

Each item of the sensory test will be assessed according to the following criteria.

- 0: No abnormality
- 1: Weakening or disappearance in the fingers or toes
- 2: Weakness or disappearance up to the wrist or ankle
- 3: Decreased or disappeared up to the forearm or lower leg
- 4: Weakness or disappearance in the upper arm or thigh

Reflex function will be assessed according to the following criteria.

- 0: No abnormality or increased
- 1: Decreased
- 2: Elimination

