11.2 Significant Adverse Events

For the purpose of examining the safety profile, AEs of special interest are defined as follows.

- (1) Renal disorder
Serum creatinine >2.0 mg/dL
- (2) Drug-induced liver injury
¹⁹ if all of the following definitions of Hy's law are met:
 - a) AST or ALT $> 3 \times$ ULN
 - b) Total bilirubin > 2 times the upper limit of normal
 - c) ALP $< 2 \times$ ULN
 - d) There is no explanation for the above laboratory abnormalities a), b), and c) other than investigational product.
- (3) Neurological disorders (medically significant changes on neurological examination in the healthy side)

If such an adverse event occurs, the investigator must inform the monitor immediately about the situation. The monitor will confirm with the investigator (subinvestigator) whether or not the study can be continued.

For significant adverse events, the sponsor will appropriately evaluate the occurrence status and frequency, and examine the appropriateness of study continuation and the necessity of protocol amendment.

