13.3.3 Safety

The number and proportion of subjects with adverse events, adverse reactions, serious adverse events, and serious adverse reactions will be tabulated by SOC and PT for each group.

For each laboratory, vital sign, and ECG parameter, summary statistics (Mean, standard deviation, minimum, median, maximum) by treatment group and measurement time point, and summary statistics of differences from baseline will be presented.

For neurological examination, shift tables of changes from the onset to Day5 will be presented by group and measurement time point.

For urinalysis, shift tables of changes from baseline will be presented by group and measurement time point.

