13.4 Changes in the statistical analysis plan

If the statistical analysis plan described in this section is changed before data lock, the reason for the change will be described in the statistical analysis plan and the clinical study report. If the analytical method is changed or an additional analysis is performed after data lock, the reason will be described in the statistical analysis plan and the clinical study report to distinguish it from the results of the planned analysis.

14. Compliance with, Deviations from, or Changes in the Protocol

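### The SAP drops three by-group safety outputs that the protocol pre-specifies (neurological shift tables, and SOC/PT tables of serious adverse events and of serious adverse reactions) without declaring it

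*SAP*

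**What the plan says.** Protocol 13.3.3 sets out the safety outputs. For adverse events it names four classes, and the sentence ends: "serious adverse events, and serious adverse reactions will be tabulated by SOC and PT for each group". For the neurological examination it states: "For neurological examination, shift tables of changes from the onset to Day5 will be presented by group and measurement time point". Protocol 5.4.2 explains why the examination is a safety endpoint. Delayed neurotoxicity had been seen in nonclinical studies, so "a neurological examination was included to check for the development of symptoms due to neuropathy of peripheral nerves and notochord".

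Protocol 9.2.4.1 schedules a "neurological examination on the healthy side once from the onset to Day5, and then on Day14, Week 3, at the time of discharge", and again at 3 months. Five sensory items are graded 0 to 4 and four reflex items 0 to 2, and "the date and results will be recorded in the CRF". Protocol 11.2 lists among its adverse events of special interest: "Neurological disorders (medically significant changes on neurological examination in the healthy side".

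If the planned analysis changes before data lock, Protocol 13.4 requires that "the reason for the change will be described in the statistical analysis plan and the clinical study report".

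In the SAP, section 7.3.6 reads in full: "Neurologic Examination data will be listed". Section 7.3.1 plans SOC/PT summaries for all and for related treatment-emergent adverse events (TEAEs), plus the proportion of subjects with any serious TEAE. Section 8 declares two changes: the per protocol set is dropped, and efficacy is summarised descriptively without tests.

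**The concern.** Three by-group outputs promised in the protocol have no counterpart in the SAP, and nothing in the SAP says they were removed. Under the SAP as written, the study report need contain no summary by arm of the graded neurological findings. Nor need it summarise by arm which serious events, or which serious reactions, occurred.

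The neurological omission weighs most, because the examination targets a known nonclinical signal. Changes judged medically significant become adverse events and reach the TEAE tables. Smaller graded changes can be found only by reading the listing subject by subject, so a mild shift spread across one arm would be easy to miss. SAP 4.1 plans no DSMB, which makes the by-arm account in the final report more important.

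**Working it through.** No sample size, power or error-rate figure bears on this point. The check sets Protocol 13.3.3 against SAP 7.3.1 to 7.3.6, the output lists in SAP 14.1 and 14.2, and the declarations in SAP 8 and SAP 10.

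| Output named in Protocol 13.3.3, by group | Planned in the SAP? |
|---|---|
| Adverse events by SOC/PT | Yes, 7.3.1 and Table 14.3.1.2 |
| Adverse reactions by SOC/PT | Yes, 7.3.1 and Table 14.3.1.3 |
| Serious adverse events by SOC/PT | No; one overall proportion (7.3.1) and a seriousness field in the listing |
| Serious adverse reactions by SOC/PT | No summary of any kind |
| Laboratory summary statistics | Yes, 7.3.2 and Tables 14.3.2.1 and 14.3.2.2 |
| Vital signs summary statistics | Yes, 7.3.3 and Table 14.3.3.1 |
| ECG summary statistics | Yes, 7.3.4 and Table 14.3.4.1 |
| Neurological examination shift tables | No; Listing 16.2.7.1 only |
| Urinalysis shift tables | Yes, 7.3.2 and Table 14.3.2.6 |

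- **Requested:** 4 SOC/PT tables + 3 sets of summary statistics + 2 sets of shift tables = 9.
- **Planned:** 2 + 3 + 1 = 6.
- **Missing:** 9 − 6 = 3, and 3/9 = 33%.
- **Declared in SAP 8:** 2 changes, of which 0 concern these 3 outputs.
- **Safety endpoints:** Protocol 5.4.2 lists 5. Adverse events, laboratory tests, vital signs and ECG each have a planned summary; the neurological examination has none.
- **SAP 10 (data not summarised or presented):** marked not applicable, although the neurological data are not summarised.

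Three readings could have closed the gap.

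1. *By-group wording.* SAP 7.3.3 and 7.3.4 mention only the analysis visit for vital signs and ECG. SAP 13 makes treatment group the default for summary tables, so these count as planned.
2. *Non-exhaustive list.* SAP 14 calls its list a minimum. It also says that a complete list should be included in the SAP, and the body text of 7.3.1 and 7.3.6 does not plan the three outputs either.
3. *Early termination.* SAP 8 gives it as the reason for the two declared changes only. SAP 14.2 still plans three laboratory shift tables (14.3.2.4 to 14.3.2.6). The protocol asked for the urinalysis one; haematology and biochemistry were added. Shift tables were therefore not ruled out as a format.

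**The case against.** The strongest reply is that little information is lost. Every adverse event is listed with treatment, seriousness and relationship, and SAP 13 orders listings by treatment. Each serious TEAE is counted in the general TEAE table, and each serious reaction also in the adverse reaction table, though neither table marks seriousness. Neurological results are listed in full. SAP 1 says the whole plan is executed on a limited sample with exploratory results, and the documents do not give the number enrolled. Nobody can therefore show that sparse shift tables would tell more than a listing. This stands as a limit on the harm. It does not meet Protocol 13.4, which requires the reason for a change to be stated.

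The percentage depends on the counting rule. Protocol 13.3.3 can also be read as four statements (adverse events; laboratory, vital signs and ECG; neurological examination; urinalysis). On that count one is wholly unmet and one is half met. The three named outputs are absent either way.

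The neurological reference is also awkward. It may be taken as late as Day 5, after the 72-hour infusion, so a shift from it need not show change from an untreated state. SAP 6 defines baseline as the last assessment before dosing, while footnote ** of Appendix 1 makes an exception for this examination. The protocol's phrase about onset to Day 5 is itself loose. Only one examination is scheduled in that period, however, so the natural reading is that it serves as the reference. This limits interpretation and calls for a flag on late references; it does not justify leaving the tables out.

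**Conclusion.** The concern holds. Three of the nine by-group safety outputs named in Protocol 13.3.3 are missing from the SAP, and none of the three omissions is declared. The count takes each adverse event class, each type of summary and each type of shift table as one output. The conclusion rests on the body text and output lists of the SAP as available; the study report and the content of the data review meeting cited in the SAP revision history were not available.

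The consequence is confined to descriptive safety reporting and to an undeclared departure from the protocol. The point should be corrected, with the neurological tables first and the two serious-event tables second.

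**What to change.** 1. In SAP 7.3.6 and 14.2, restore shift tables for each sensory and reflex item, by treatment group on the safety population. They run from the single examination up to Day 5 (the Appendix 1 reference) to Day 14, Week 3, discharge and Month 3. State that this reference departs from the general baseline rule in SAP 6, and use the recorded examination date to flag references taken after Day 1.
2. In SAP 7.3.1 and 14.2, add SOC/PT tables by arm for serious TEAEs and for serious adverse reactions.
3. If any of the three is left out on purpose, say so with the reason in SAP 8, and correct SAP 10 if neurological data remain unsummarised.

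The cost is table programming and a few lines of text. The neurological set is the largest: 5 sensory + 4 reflex = 9 items, over 4 later visits, gives 9 × 4 = 36 item-by-visit panels per arm. Neurological results and dates, seriousness and causality are already in the CRF, so no new data are needed and there is no burden on patients. Declaring an omission instead costs about one line in SAP 8, but it cures only the missing declaration and leaves the by-arm summaries absent.

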8. CHANGES FROM THE PROTOCOL

MTPC has decided that this study is prematurely terminated due to reconsideration of the MTPC's product pipeline. Therefore, the stasitical analysis plan is changed form the protocol as follows.

- Per protocol set will be excluded from the analysis populations.
- Efficacy endpoints will be only descriptively summarized without any formal statististical test.

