1. INTRODUCTION

This statistical analysis plan (SAP) is based on the final protocol version 01.01 dated 1 August 2017. The plan covers statistical analysis, tabulations and listings of efficacy and safety data to investigate the efficacy and safety of MCI-186 (bolus followed by 72-hour continuous infusion) in acute ischemic stroke patients through a double-blind, parallel-group comparison with the existing MCI-186 dosing regimen as the control.

The SAP is prepared by Mitsubishi Tanabe Pharma Corporation(MTPC), Data Science Department. The statistical analyses and production of the outputs described in the SAP will be conducted and QC checked by [REDACTED] Medical Development Business Department2 SAS Consulting Group, using SAS® 9.3 or later Software. The final analyses and outputs will be approved by Mitsubishi Tanabe Pharma Corporation, Data Science Department.

MTPC has early decided to stop subjects's recruitment based on internal decision. Therefore, the planned sample size will not be completed so that this plan will be executed based on a limited available sample size. The finding for this statistical analysis will lead to exploratory results.

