2. STUDY OBJECTIVE(S) AND ENDPOINTS

2.1 Study Objective(s)

To investigate the efficacy and safety of MCI-186 (bolus followed by 72-hour continuous infusion) in acute ischemic stroke patients through a double-blind, parallel-group comparison with the existing MCI-186 dosing regimen as the control.

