3.2 Schedule of Study Procedures

Study assessments are summarized in the Time and events schedule (Table 1).

Table 1: Assessment and Observation Schedule

Assessment Time Point	Before Treatment Initiation		Study Drug Treatment Period							Observation period					
	Consent	Confirmation of suitability	Registration	Day 1	Day 2	Day 3	Day 4	Day 5	Day 7	Day 10	Day 14 or study drug treatment period discontinuation ^a	After 3 weeks ^b	At discharge	After 3 months ^c or at observation period discontinuation	
Allowable Range										± 1 day	± 1 day	+1 day	± 2 days	-1 day	± 8 days (+8 days)
Consent acquisition	●														
Subject background		●													
Registration/allocation			●												
Study drug treatment				72-hour continuous infusion							Twice a day for 14 days ^d				
NIHSS		●		Assessments performed every day for 7 days after treatment initiation							●	●	●	●	●
mRS ^e		● ^f										●	●	●	●
BI												●	●	●	●
FIM												●	●	●	●
Diagnostic imaging		DWI T2*WI FLAIR MRA					DWI ^g T2*WI ^g				DWI T2*WI				FLAIR
Neurological assessments				● ^h							●	●	●	●	●
Standard 12-lead ECG	●						● ⁱ								
Vital signs	●						● ⁱ		●		●				
Clinical laboratory tests (centralized measurements)	●						● ⁱ		●		●		●	●	
Clinical laboratory tests (site measurements)		● ^j		Measured every day for 5 days after treatment initiation ^k											
PGx blood sample collection				● (Blood samples will be collected during the study from subjects who have consented to having blood samples collected for genetic analysis)											
Adverse events															
Concomitant medications															

- a) If the study is discontinued during the study drug treatment period, the tests that are stipulated should be conducted at study drug treatment period discontinuation will be conducted, and whenever possible subject safety will be evaluated at 3 months after onset.
- b) In this study, "after 3 weeks" is defined at Day 22. If a subject is discharged within 3 weeks after treatment initiation, then the tests that are stipulated should be performed at discharge will be performed, and the tests that are scheduled for after 3 weeks will not be necessary.
- c) In this study, after 3 months is defined as Day 85. If the study is going to be discontinued during the observation period, then the tests that are stipulated should be conducted at observation period discontinuation will be conducted, and subject safety will be assessed after 3 months whenever possible.

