4.2 Interim Analysis

No interim analysis will be performed for this study.

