6. GENERAL CONSIDERATIONS

Efficacy endpoints will be analysed on the FAS population and listed on the FAS population. Subjects will be analysed according to the treatment group they were randomised to. Safety analyses will be performed on the SAF. Subjects will be analysed according to the treatment group they were actually received.

In general, continuous variables will be summarized descriptively using the number of observations (n), mean, standard deviation (SD), median, minimum and maximum. Categorical variables will be summarized using frequency counts and percentages. The denominator for the percentages will be the total number of subjects in the relevant group and population (analysis set) being presented, unless otherwise specified (e.g., on some occasions, percentages maybe calculated out of the total number of subjects with available data at a particular visit and/or time point).

For each section, baseline is the last valid assessment prior to the start of IMP administration. For numerical variables, change from baseline will be calculated as the post-baseline value minus the baseline value. If baseline value cannot be determined for a particular variable, change from baseline will not be calculated.

Data will be handled as follows.

(1) Definition of missing data

When test values are missing, or could not be measured because of, for example, a problem with the test sample, these values will be handled as missing. In addition, no imputation will be made in case of missing values.

(2) Handling of the data at measurement time points

When summarizing the data at each measurement time point, data within the analysis time windows defined in Appendix 1 will be used. If multiple values were obtained within the time window, then the value closest to the planned assessment day will be used.

Unscheduled visits will not be displayed in by-visit summary tables, but will be included in the data listings.

Listings will include scheduled, unscheduled, retest and early discontinuation data.

The date and times of start and end of IMP administration will be taken from the Electronic Case Report Form (eCRF) Dosing form.

All medical history and adverse events will be coded from the actual term using the Medical Dictionary for Regulatory Activities (MedDRA) version 20.0.

All prior and concomitant medications will be coded using the World Health Organization (WHO) drug dictionary (Version: WHO DDE B2 Mar_2017).

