7.2.1.1 Adjustment for Covariates

Adjustment for covariates will not be performed.

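### The stopped trial's SAP drops estimation along with testing, so no visible efficacy output gives a between-arm contrast or its precision

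*SAP*

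**What the plan says.** **Protocol 13.3.1 and 13.3.2.** The primary analysis compares the arms on time to an NIHSS improvement of 4 points or more, scored daily to Day 7, with a log-rank test stratified by the randomisation factor. A Cox model with group and allocation factor then gives a hazard ratio, 95% CI and p-value. The secondary clinical endpoints and the three imaging measures each get a between-group difference with a 95% CI. The definition of censoring is left to the SAP.

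**SAP.** The Introduction reports that recruitment stopped early and the sample is limited: "The finding for this statistical analysis will lead to exploratory results". Section 8 gives a reconsideration of the product pipeline as the reason and lists two changes. The per-protocol set goes, and "Efficacy endpoints will be only descriptively summarized without any formal statististical test". Section 7.2.1.1 adds: "Adjustment for covariates will not be performed". Sections 7.2.2 and 7.2.3 plan descriptive statistics or counts by arm, and efficacy tables 14.2.1.1 to 14.2.1.9 are all summaries. The objective in 2.1 is still to investigate efficacy and safety "through a double-blind, parallel-group comparison with the existing MCI-186 dosing regimen as the control". The exploratory endpoint text is not visible and cannot be judged.

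**The concern.** A hazard ratio or a difference with a confidence interval is an estimate and needs no hypothesis test. The stop and the limited sample explain why a confirmatory test was abandoned, but they do not require the estimates to be abandoned too. Without them, a reader sees columns of by-arm figures and must judge by eye how far apart the arms are and how uncertain that gap is. In a small trial, bare means and percentages hide the imprecision that an interval would show. The primary endpoint suffers most, because its time-to-event form disappears from the planned tables altogether.

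**Working it through.** **1. The plan's own figure.** Protocol 5.3.2 allocates 5:4:5 and 6.1 plans 336 subjects. 336 × 5/14 = 120, 336 × 4/14 = 96 and 336 × 5/14 = 120, so the planned arm sizes reproduce. The assumptions behind the 96 per group are not visible and cannot be recomputed. The achieved numbers are not stated.

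**2. The two documents side by side.**

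| Endpoint | Protocol 13.3 | Visible SAP 7.2 and 14.2 |
|---|---|---|
| NIHSS to Day 7 (primary) | log-rank test; hazard ratio, 95% CI | by-arm values and changes by visit |
| NIHSS at later visits | difference, 95% CI | by-arm statistics; count and % improved by ≥4 |
| mRS | difference in proportion 0 or 1, 95% CI | by-arm count and % for each score |
| BI, FIM | difference, 95% CI | by-arm statistics; BI categories |
| Rehabilitation start, hospital stay | difference, 95% CI | by-arm statistics |
| Infarct volume, edema, hemorrhage | difference, 95% CI | by-arm statistics |

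Every protocol endpoint shown has a planned between-arm estimate. None has one in the visible SAP.

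**3. What a reader could recover.** For most secondary endpoints, n, mean, SD and counts by arm are enough for a crude difference and interval. For time to first improvement they are not:

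- The percentage improved at each visit is not cumulative. A patient who gains 4 points on Day 3 and loses them by Day 4 is an event in a survival analysis but a non-responder at Day 4.
- NIHSS is scored on Day 6 (SAP Table 1: "Assessments performed every day for 7 days after treatment initiation"), but Appendix 1 has no Day 6 visit. Day 6 falls in the Day 7 window [6, 8], where "If multiple values were obtained within the time window, then the value closest to the planned assessment day will be used", so a Day 7 score displaces it.
- The event times survive in patient listing 16.2.5.1, because "Listings will include scheduled, unscheduled, retest and early discontinuation data".

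**4. Precision of a restored hazard ratio.** The 95% CI multiplies and divides the estimate by exp(1.96 × √(2/e)), where e is the events per arm, n × event rate. All n and rates are assumptions.

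| n per arm | 30% events | 50% | 70% |
|---|---|---|---|
| 5 | 9.61 | 5.77 | 4.40 |
| 10 | 4.95 | 3.45 | 2.85 |
| 20 | 3.10 | 2.40 | 2.10 |
| 30 | 2.52 | 2.05 | 1.83 |

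The formula takes equal arms and no stratum adjustment. Under 5:4:5, 20 controls would go with 16 in L. At 50% events that gives exp(1.96 × √(1/10 + 1/8)) = 2.53, so unequal allocation changes little.

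**5. Whether it can be estimated.** With event rate p, one comparison fails if either arm has no event: 1 − (1 − (1−p)^n)². At p = 0.3 this is 31% at 5 per arm, 5.6% at 10 and 0.2% at 20. At p = 0.5 it is 6.2%, 0.2% and under 0.1%. At least one of the two hazard ratios fails if any of the three arms has no event. At 5 per arm and p = 0.3 that is 1 − (1 − 0.7⁵)³ = 1 − 0.832³ = 42%.

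**6. Precision of restored differences at 20 per arm.** For a mean, t(0.975, 38) × SD × √(2/20) gives 2.6 NIHSS points for a change SD of 4 and 3.8 for an SD of 6. For responders, 1.96 × √(2p(1−p)/20) gives 28 percentage points at p = 0.3 and 31 at p = 0.5.

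**7. Number of intervals.** Per comparison: NIHSS 7, mRS 3, BI total 4, BI categories at least 4, FIM (total, motor, cognitive) 9, rehabilitation 1, stay 1, imaging at least 3, which makes 32. Two comparisons give 64, and two hazard ratios make 66. If the arms do not differ, about 66 × 0.05 = 3.3 would exclude no effect by chance.

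**The case against.** The strongest reply is that the change is disclosed, reasoned and sensible. SAP Section 6 defines a descriptive summary as n, mean, SD, median, minimum and maximum, or counts and percentages. The protocol itself lists descriptive statistics separately from differences and intervals. Read with 7.2.1.1, Section 8 therefore excludes contrasts and the adjusted Cox model. Termination, limited sample and exploratory status are reasons, and Protocol 13.4 asks for a reason, not an itemised list. All of this stands.

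Several stronger readings are tempting, and the documents do not support them:

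- A reader might infer that the estimates were dropped silently or in breach of Protocol 13.4. They were not; naming each dropped analysis would be good practice only.
- A reader might infer from the decimal-place rule for confidence intervals in SAP Section 13 that intervals were still intended. That table is unedited template text. It also formats p-values and mentions PK parameters, neither of which applies here, so it shows nothing about intent.
- A reader might infer that imaging analysis was dropped because no imaging table is listed. Section 7.2.3 still plans it, and Section 14 calls its list a minimum.
- A reader might say that the arms are not compared at all. By-arm columns can be read side by side; what is missing is an estimated contrast.

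It is also fair that every precision figure rests on assumed numbers, and that adjusting for three NIHSS strata may be unworkable in a very small sample. The reply does not show why a descriptive report must omit intervals that can be computed.

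**Conclusion.** The point holds as a modest, inexpensive improvement, not as an error in the plan. Dropping formal tests is justified; dropping the estimates as well is not needed for that, and it leaves a comparative objective without any visible estimate of a contrast. The loss is moderate for most secondary endpoints and larger for the primary endpoint, whose event times remain only in a patient listing.

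A reader might suspect that the stop followed efficacy results, which would make estimates hard to interpret. The documents give no support for that: the stated reason is the pipeline, and "No interim analysis will be performed for this study". Exploratory estimates would be imprecise but interpretable.

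The comparison of the two documents is firm for the visible text. The size is conditional. Achieved numbers are absent, and the range of 5 to 30 per arm and the event rates and SDs are assumptions. Under them, the hazard ratio's interval runs from a factor of about 1.8 each way (30 per arm, 70% events) to 9.6 (5 per arm, 30% events).

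**What to change.** Keep the absence of formal tests and the exploratory label. Restore, without p-values:

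- **Hazard ratio with 95% CI** for time to first NIHSS improvement of at least 4 points up to Day 7, H versus control and L versus control, using every daily score including Day 6. State a censoring rule, for example at the last NIHSS up to Day 7. Adjust for the enrolment NIHSS strata only if numbers allow, and amend 7.2.1.1 accordingly. Report it only where each compared arm has an event and the estimate is finite.
- **Between-group differences with 95% CIs** for the secondary and imaging endpoints, as in Protocol 13.3.1(2) and 13.3.2. Label them as exploratory, unadjusted for multiplicity and not to be read as tests.

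A sentence in Section 8 saying which protocol estimates are kept would help. If data lock has passed, Protocol 13.4 already requires that added analyses be explained and kept distinct from the planned ones.

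The cost is programming for 2 hazard ratios and about 64 differences from data already collected. The downsides are possibly very wide intervals, one or both hazard ratios not estimable at very small numbers, and about 3 of some 66 intervals excluding no effect by chance.
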